Risks related to the other study procedures (blood drawing, six minute walk testing, quality of life surveys) are generally low and will be minimized by following routine precautions for blood drawing, by monitoring oxygen saturation, heart rate and patient wellbeing during walk testing, and by reminding patients that continued participating in the study is voluntary. Patients are asked to stop walking if they feel dizzy, develop severe dyspnea, or develop chest pain, or if they appear unsteady. They are monitored closely by a trained operator during the test. Patients will also be told they can refuse to answer any questions that make them uncomfortable.

Confidentiality:

Protected health information will be collected during the study. This will be protected in locked cabinets within locked offices, and by use of password protected computers in locked offices. Study samples will be stored within research freezers and identified with subject study numbers only.

Decompensation related or unrelated to study medication: worsening pulmonary hypertension is always a possibility and a concern. Patients will be receiving closer than usual monitoring through more frequent visits and right heart catheterizations. However, decompensation may occur. Any patient with clinical worsening who requires additional therapies will be withdrawn from the study, after undergoing an early "end of study" visit, when it is felt to be safe to do so and when they are willing. Additional therapy, as appropriate, will then be considered.

Other Potential Problems: Completion: we need 16 patients to undergo a post-treatment right heart catheterization and other week 24 assessments out of a planned enrollment of 18 patients. This allows for 2 (12.5%) patients to drop out *without* a post-Rx catheterization and still have sufficient power. Based on past experience, this should be achievable: even patients leaving early typically allow end of study assessments. However, if a higher dropout rate is seen then enrollment will be increased so as to allow 16 patients to complete. Safety: because these patients are sick at baseline, adverse events from the disease are not unexpected. We will regularly review adverse events (AE) in order to identify any concerns, and a data safety monitory committee will review the AE and SAE data prior to each IRB continuing review.

Data and safety monitoring plans:

Monitoring will include:

- 1. Principal investigator: As the principal investigator, I will have the primary responsibility for the safe conduct of the study. This will include careful conduct of the study, close monitoring for any adverse effects, and frequent follow-up.
- 2. Institutional review board (IRB): the UTSW IRB will monitor the studies through approval of the protocol prior to any patient enrollment, through routine review of any serious adverse events, and through general oversight of all research conducted at UT Southwestern.
- 3. Internal safety physician: A local safety monitoring physician is planned. This physician will be independent from the conduct of the study. A charter outlining responsibilities will be created. All SAEs will be reviewed. Every 6 months, all SAEs along with a tabulated chart of all AEs every 6 months (tabulated and stratified by group assignment). Adverse events will also be reported to the NIH and IRB, as required.

Statistical Analysis

Aim 1: To determine whether fluoxetine lowers pulmonary vascular resistance in patients with pulmonary arterial hypertension by conducting an open-label clinical trial

- 1. Study design and measurements: 18 patients will receive on fluoxetine for \24 weeks. Patients will undergo a right heart catheterization, 6MWD testing, QIDS-SR depression scale testing, SF-36, other quality of life (as above) and functional class assessment pre-treatment and after 24 weeks.
- 2. Efficacy endpoints: Primary endpoint: Change in PVR between baseline and end of study. Secondary endpoints include change in: RA, PA and wedge pressure, CO, SvO2, PVR (Fick), QIDS-SR, SF-36, systemic BP and HR, functional class and change in 6MWD.
- 3. **Safety and tolerability endpoints:** will be assessed by tabulating adverse events and by determining the number of patients tolerating each dose of fluoxetine.
- 4. **Open label** hemodynamics after one year will also be presented descriptively and vs. baseline among patients who undergo a one-year right heart catheterization.
- 5. **Comparisons and evaluation of the data:** All statistical testing will be baseline vs. follow-up at 24 weeks. Student's t-tests will be used for significance testing if the data are normally distributed with no missing data. If data are missing due to dropouts or lack of study completion, patients with worsening symptoms will be assigned worst rank, and a Wilcoxon rank sum test will be used. The Wilcoxon rank sum test will also be used to evaluate the ordinal results from the QIDS-SR, the SF-36, and changes in WHO functional class.
- 6. Assumptions and anticipated magnitude of treatment effect and power: Baseline PVR is estimated to be 9 wood units, based on preliminary data PVR of 8.4 wood units as well as other similar trials. Effect size: this study will be powered to detect a 20% improvement in fluoxetine patients with 16 of 18 patients undergoing an end of study right heart catheterization. In earlier studies, approved PAH therapies (endothelin-1 antagonists, PDE-5 inhibitors and prostacyclins) have lowered PVR 12-39% (all except one: 20-39%). We also anticipate a standard deviation of 20% of baseline PVR.

Summary: With 16 patients completing, this study will have 80% power (α =0.05) to detect a between-group difference assuming 20% improvement with fluoxetine (References for SD and other assumptions: [41-47])

Safety and tolerability endpoint: An important secondary endpoint will be safety and dosing tolerability. This will be evaluated both qualitatively and quantitatively. We anticipate that \geq 80% of patients will be able to complete the study (completing either 24 weeks or undergoing early end of study) and \geq 70% of enrolled patients will complete it without suffering a serious adverse event judged as possibly or likely related to medication (SAE; death, hospitalization, risk to life or permanent disability). The determination of "likely" related is to be made by an independent

physician who will review the data for all SAEs. These modest goals are chosen because all patients will be seriously ill.

Investigational New Drug (IND) Exemption:

The fluoxetine clinical trial should be IND exempt based on our discussions with the FDA. For the pilot study (completed) we proposed exemption, but the UTSW IRB requested IND submission to be certain criteria 3 was met; this was done and the FDA classified it as IND exempt. We therefore anticipate similar classification with the slightly larger study as it will still be small and not seeking a new indication. Specific criteria we meet include:

IND exemption criteria:

(1) it is not intended to be reported to FDA in support of a new indication for use or to support any other significant change in the labeling for the drug;	As a small study looking at a surrogate endpoint (change in PVR), this will not support a label change or new indication.
(2) it is not intended to support a significant change in the advertising for the product;	Same as response to (1)
(3) it does not involve a route of administration or dosage level, use in a subject population, or other factor that significantly increases the risks (or decreases the acceptability of the risks) associated with the use of the drug product;	The pilot study of fluoxetine and reserpine (see preliminary data section) met this criteria, per FDA response to our IND application. The fluoxetine study alone has a similar or lower risk (because only fluoxetine is used) and should therefore be similarly exempt.
(4) it is conducted in compliance with the requirements for IRB review and informed consent [21 CFR parts 56 and 50, respectively];	IRB review is being obtained for the clinical trial.
(5) it is conducted in compliance with the requirements concerning the promotion and sale of drugs [21 CFR 312.7];	Use of fluoxetine will be investigational; promotional claims of safety and effectiveness for PAH will not be made
(6) It does not intend to invoke 21 CFR 50.24.	vve will obtain informed consent

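### The stated power with two patients lost leaves out the plan's own worst-rank rule; with two worst-ranked losses the named rank sum test has about 43-70% power, not 80%

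*Combined protocol and SAP*

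**What the plan says.** The Completion paragraph, under Other Potential Problems, requires 16 of 18 enrolled patients to have a follow-up catheterization. It says two can be lost without "a post-Rx catheterization and still have sufficient power". If more are lost, "enrollment will be increased so as to allow 16 patients to complete".

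Statistical Analysis, Aim 1, item 6 gives the matching figure: "With 16 patients completing, this study will have 80% power". Its inputs are a baseline PVR of 9 Wood units, a 20% fall ("this study will be powered to detect a 20% improvement in fluoxetine patients with 16 of 18 patients") and an SD: "We also anticipate a standard deviation of 20% of baseline PVR".

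Item 5 sets the analysis. A t-test applies only to normally distributed data with nothing missing. If data are missing through dropout or non-completion, "patients with worsening symptoms will be assigned worst rank, and a Wilcoxon rank sum test will be used".

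The plan allows a worsening patient to have no follow-up PVR. The paragraph on decompensation withdraws patients who worsen and need added therapy, with an exit visit only when safe and acceptable to the patient. The Early withdrawal paragraph under Study Methods lets a patient decline the exit catheterization. The Dose selection paragraph expects about 10-20% dropout, which is 1.8 to 3.6 of 18 patients.

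**The concern.** The power statement and the analysis rule describe different data sets when a worsening patient is lost. The first counts 16 patients and stops. The second analyses those 16 plus each worsening loss, placed at the unfavourable extreme, where a rank test is most affected. The power statement is silent on this, and so is the rule for replacing dropouts.

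PVR is the only primary endpoint and there is no control arm. If the trial ended with 16 catheterized and two worst-ranked, the protocol would call it adequately powered and a null result would be read in that light. The actual power could be well below the figure given.

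**Working it through.** **Inputs.** The fall is 20% of 9 = 1.8 Wood units and the SD is 20% of 9 = 1.8, so the standardized effect is 1.0 (item 6). Alpha is 0.05. Sidedness is not stated; I take it as two-sided because that reproduces the plan's figure. All tests compare baseline with week 24 in one group ("All statistical testing will be baseline vs. follow-up at 24 weeks"), although the power summary speaks of groups: "80% power (α =0.05) to detect a between-group difference".

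**Step 1: the plan's own figure.** Treat baseline and follow-up as two independent sets of 16 values.

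- Noncentrality = 1.8 / (1.8 × √(2/16)) = 2.83.
- Normal approximation: Φ(2.83 − 1.96) = Φ(0.87), giving 80.7%. Noncentral t with 30 df: 78.1%.

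So the stated 80% reproduces, for a complete-data two-sample test with no worst ranks. A one-sided t-test would give 86.8%.

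**Step 2: add the worst ranks.** Simulated power of the rank sum test (independent sets, continuity correction). The exact signed-rank test on paired changes (SD of change 20%) is shown for comparison. It suits the data but the plan does not name it.

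| 16 completers averaging a 20% fall, plus | Rank sum (named) | Signed-rank (not named) |
|---|---|---|
| 0 worst ranks | 75% | 95% |
| 1 worst rank | 61% | 76% |
| 2 worst ranks | 43% | 28% |
| 3 worst ranks | 25% | 0% |

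With two worst ranks, the rank sum figure stays at 42-43% for within-patient correlations from 0 to 0.8.

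*Hand check, rank sum, two worst ranks.* There are 18 × 18 = 324 follow-up/baseline pairs. Under the null, the number of pairs with follow-up higher has mean 162 and SD √(18 × 18 × 37/12) = 31.6. Significance needs a count of at most 162 − 1.96 × 31.6 − 0.5, that is 99. The two worst-ranked patients use 2 × 18 = 36, leaving 63. The 16 completers give 16 × 18 = 288 pairs, each with follow-up higher with probability Φ(−1/√2) = 0.24, so about 69 are expected. As 69 exceeds 63, power must be somewhat below one half, in line with 43%.

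*Hand check, signed-rank.* At n = 18 the two-sided 5% critical value is 40. Two worst ranks use 17 + 18 = 35, leaving 5 for every other patient whose PVR rose. At n = 19 the critical value is 46 and three worst ranks use 17 + 18 + 19 = 54.

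**Step 3: change who carries the 20% fall.** Step 2 gives the completers the full 20% and adds the lost patients on top, so the average across everyone treated is below 20%. Suppose instead that the 20% fall and 20% SD hold across all 18 and that the lost patients are those with the worst values.

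| All 18 average a 20% fall | Rank sum | Signed-rank |
|---|---|---|
| 1 worst-ranked (17 completers) | 77% | 95% |
| 2 worst-ranked (16 completers) | 70% | 79% |

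**Step 4: losses that are not worsening.** If the two lost patients have no worst rank and only their follow-up values are absent (18 baseline against 16 follow-up), rank sum power is about 77%.

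**Step 5: replacement of dropouts.** Two losses do not trigger the rule. With three, the plan enrols until 16 complete, but the three lost patients remain in the analysis if worst-ranked: 25% by rank sum under the Step 2 assumption. Under that same assumption, 80% with two worst ranks would need about 26 completers by rank sum (81%) or 22 by signed-rank (82%).

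**The case against.** The strongest reply is that low power here needs several things at once. Both losses must be worsening patients, both must lack a catheterization, and the completers alone must average a 20% fall. Item 6 powers for a 20% improvement in fluoxetine patients, which can fairly be read as all those treated; on that reading the named test keeps about 70%. Patients leaving for side effects or withdrawn consent are not worst-ranked. The one fluoxetine withdrawal in the pilot was for anxiety and poor sleep, and the sponsor's experience is that early leavers usually allow the final assessments. Worst-rank scoring is also meant to be conservative.

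Most of this stands, and it bounds the point. A reader might infer that a drug truly lowering PVR by 20% would probably be declared ineffective once two patients are lost. The documents do not support that: it follows only under the Step 2 assumption, and nothing in them says how likely two worsening losses without catheterization are. A reader might also infer that three such losses rule out a significant result, or that about 80% survives one. The first is true only of the signed-rank test. The second comes nearest with the signed-rank test (76% or 95%); the named test gives 61% or 77%, depending on the assumption.

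What does not stand is that the text is adequate as written. Under either assumption, the named test with two worst ranks falls short of the stated 80%, and the plan gives no sign of it.

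**Conclusion.** The point holds in a limited form. The 80% is arithmetically sound for complete data in 16 patients, but it is not the power of the specified analysis when a lost patient is worst-ranked. With two such losses the named rank sum test has about 43-70% power, depending on whether the 20% fall belongs to the completers or to all 18 patients. The signed-rank range is about 28-79%. Without worst-ranked losses the claim is roughly right (75-77% by rank sum).

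These figures assume a 20% fall, SD 20% and two-sided 0.05, with baseline and follow-up treated as independent for the rank sum test and the SD applying to the change for the signed-rank test. One-sided testing at 0.05 would give about 59% for either test with two worst ranks under the Step 2 assumption, still below 80%.

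It would be too strong to say that added enrolment cannot restore power. The plan's rule of stopping at 16 completers does not do so; going further could. Severity is moderate: a stated figure needs qualifying, and the design is not invalidated.

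**What to change.** In the Completion paragraph and in Aim 1 item 6, replace the assurance of sufficient power and the single 80% figure with a short table of power for 0, 1 and 2 worst-ranked losses. Calculate it for the test that will be used, and name that test. For the rank sum test as now written, the entries are about 75%, 61% and 43% if 16 completers average a 20% fall, with 77% (one loss, 17 completers) and 70% (two losses) if the fall holds across all 18. State the assumptions, including sidedness and what the 20% SD refers to.

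Add two sentences. The first should say that the stated power applies when losses are not worst-ranked. The second should say that enrolling until 16 complete does not by itself preserve power when losses are worst-ranked, because those ranks stay in the analysis.

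The cost is protocol and SAP wording only, and a less favourable stated power. This wording change requires no added patients, procedures or analyses.

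### Statistical Analysis, Aim 1, item 5 names the two-sample Wilcoxon rank sum test for a one-arm, before-after trial; a paired test is needed, and the power statement in item 6 has the same two-group form

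*Combined protocol and SAP*

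**What the plan says.** The Concise Summary describes a single open-label group of 18 patients. Under Statistical Analysis, Aim 1, item 2, the primary endpoint is "Change in PVR between baseline and end of study". Item 5 sets the frame: "All statistical testing will be baseline vs. follow-up at 24 weeks". It then gives three rules:

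- For complete data: "t-tests will be used for significance testing if the data are normally distributed with no missing data". The t-test is not said to be paired.
- For data missing through dropout or non-completion: "patients with worsening symptoms will be assigned worst rank, and a Wilcoxon rank sum test will be used". This is not limited to any endpoint, so it covers PVR.
- For scales: "The Wilcoxon rank sum test will also be used to evaluate the ordinal results from the QIDS-SR", and likewise for SF-36 and changes in WHO functional class.

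No paired rank test is named anywhere. Item 6 takes a baseline PVR of 9 Wood units (WU), a 20% improvement and 16 completers, adds "We also anticipate a standard deviation of 20% of baseline PVR", and claims 80% power at α = 0.05 "to detect a between-group difference assuming 20% improvement with fluoxetine".

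**The concern.** The rank sum test asks whether two independent samples come from the same distribution. Here there is one sample, measured twice. If the analyst works with the stated endpoint, the change, there is no second sample to rank against. If the analyst ranks baseline values against week-24 values, the test runs but treats each patient as two unrelated people, so differences between patients count as noise. The plan does not settle which analysis is done, and two analysts could report different p-values from the same data.

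The missing-data branch is foreseen. Under Other Potential Problems (Completion), the sample size has a margin for patients with no post-treatment catheterization: "This allows for 2 (12.5%) patients to drop out". One such patient is enough to move PVR off the t-test. For QIDS-SR, SF-36 and WHO class, the rank sum test is the planned method from the start. In a trial of 18 patients meant to show whether larger studies are worthwhile, the main risk is missing a real signal.

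**Working it through.** **Inputs from item 6.** Baseline PVR 9 WU; fall 20% = 1.8 WU; SD 20% = 1.8 WU; 16 completers; α = 0.05, taken as two-sided because the plan does not say. The plan gives neither the between-patient SD nor the correlation r between visits, so both are varied.

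**1. The plan's 80%.** The standardised effect is 20/20 = 1.

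- Two independent groups of 16, normal approximation: Φ(1 × √(16/2) − 1.96) = Φ(0.87) = 81%. By noncentral t: 78%.
- 16 pairs, 20% as the SD of the change: noncentral t with effect 1 gives 96%.
- 16 pairs, 20% as the SD at each visit: the effect is 1/√(2(1 − r)). Power is 75%, 80%, 88% and 96% at r = 0, 0.11, 0.3 and 0.5.

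So the stated figure has the form of a two-group calculation. It fits 16 pairs only with a per-visit SD and r near 0.11.

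**2. Rank sum against signed-rank for PVR, no missing data.** Simulation, 10,000 trials per setting.

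(A) 20% describes the change. Baseline is lognormal with mean 9 WU and values below 3 redrawn; follow-up = baseline × (1 + N(−0.20, 0.20)). The correlation implied between visits runs from about 0.6 to 0.9.

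| Assumed between-patient SD (WU) | 1.8 | 3 | 4 | 5 |
|---|---|---|---|---|
| Rank sum power | 74% | 39% | 19% | 10% |
| Signed-rank power | 94% | 94% | 93% | 93% |

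(B) 20% is the SD at each visit. Bivariate normal, means 9 and 7.2 WU, SD 1.8 WU.

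| r | 0 | 0.1 | 0.3 | 0.5 | 0.9 |
|---|---|---|---|---|---|
| Rank sum power | 75% | 76% | 79% | 82% | 94% |
| Signed-rank power | 72% | 76% | 86% | 95% | 100% |

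Under no effect, the rank sum test rejects in 0-0.4% of trials under (A). Under (B) it rejects in 4.8% at r = 0, falling to 0% at r = 0.9. The test is conservative.

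**3. Worst-rank patients under (A), added to 16 completers.**

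| Assumed between-patient SD (WU) | 1.8 | 3 | 4 | 5 | Signed-rank, all SDs |
|---|---|---|---|---|---|
| One worst-ranked: rank sum | 55% | 18% | 7% | 3% | 71-75% |
| Two worst-ranked: rank sum | 33% | 6% | 2% | 1% | about 27-29% |

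With two such patients and SD 1.8 WU, the change of test gains nothing, because the worst-rank rule itself dominates.

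**4. How often the missing-data branch applies.** The dose-selection text expects about 10-20% dropout. If every dropout lacked a follow-up catheterization and dropouts were independent, the chance of at least one in 18 would be 1 − 0.9^18 = 85% to 1 − 0.8^18 = 98%. These are upper figures, since early leavers are asked to have the procedure. Worst rank applies only to those with worsening symptoms, so the chance of a worst-ranked patient is lower again.

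**5. WHO class, illustration.** Assume 8 patients in class II and 8 in III at entry, none worsening, and all improvers moving from III to II. With two classes, the exact rank sum test equals Fisher's exact test. The exact signed-rank p for k improvers is 2 × 0.5^k.

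| Improvers | 5 | 6 | 7 | 8 |
|---|---|---|---|---|
| Rank sum p | 0.135 | 0.054 | 0.0155 | 0.002 |
| Signed-rank p | 0.063 | 0.031 | 0.0156 | 0.008 |

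The choice of test can move a result across 0.05, but the direction is not uniform. QIDS-SR and SF-36 cannot be sized, because no SDs are given.

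**The case against.** The charitable reading is that rank sum is a slip for signed-rank. Item 5 opens by saying that everything is baseline against follow-up, and an unqualified t-test in that setting is naturally read as paired. This is plausible, but the wrong name appears twice, no paired rank test appears anywhere, and item 6 also speaks of groups. Even as a slip, it leaves the analysis unsettled. The healthy controls do not supply the second sample: they complete QIDS-SR and SF-36, but they have no follow-up visit and no WHO class.

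Several points on size stand:

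- The error does not inflate false positives.
- The largest losses rest on between-patient SDs of 3 to 5 WU, which are assumptions. At 1.8 WU the loss is 94% to 74%.
- With uncorrelated visits nothing is lost, and with two worst-ranked patients the better test helps little or not at all at SD 1.8 WU.
- The WHO class example cuts both ways.

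One further point affects the correction. Model (A) puts the 20% SD on percent change, so the SD of the absolute change is about 1.9 to 2.3 WU, and a paired t-test on absolute change then has about 91-95% power. The 96% holds for an absolute-change SD of 1.8 WU, or for an analysis of percent change. The scale must therefore be stated with the power. Finally, under the SD-of-change reading the true power exceeds 80%, so the sample size is not threatened.

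**Conclusion.** The concern holds. The named test does not fit a one-arm design with a within-patient endpoint, and this is so whatever the SD or correlation. The cost is mainly lost power. For PVR with 16 completers it runs from none (per-visit SD, uncorrelated visits) to a fall from about 93% to 10% (SD of change, assumed between-patient SD 5 WU). The documents do not give the quantities needed to say where in that range the trial lies. The 80% in item 6 matches two independent groups of 16, not 16 pairs, unless 20% is the per-visit SD and r is near 0.11. This should be fixed, but it does not threaten the validity of a positive result.

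**What to change.** In item 5, call the t-test paired. Replace the rank sum test with the Wilcoxon signed-rank test on the within-patient change (week 24 minus baseline) for PVR, QIDS-SR, SF-36 and WHO class. Assign any worst rank on the change scale, in the direction of worsening.

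In item 6, replace the between-group wording with within-patient change. State whether the 20% is the SD of the change (and whether that change is absolute or in percent) or the SD at each visit with an assumed correlation. Restate the power for 16 pairs on that basis: 96% by paired t-test if the SD of the analysed change is 20%, or 75%, 88% and 96% at correlations of 0, 0.3 and 0.5 if it is per visit.

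While item 5 is open, it should also say how patients who are missing without worsening are handled, and which test applies to complete but non-normal PVR data. Renaming the test does not remove the power cost of the worst-rank rule, and the plan should acknowledge that. The cost is wording and one recalculated power figure, with no new patients, visits or data.

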This is a phase II single open-label study enrolling 18 patients with PAH. Patients will be on fluoxetine for 6 months, undergoing testing right heart catheterization at baseline or just prior to baseline and at 6 months. An estimated 3 years will be required to complete enrollment. Fluoxetine dose will be initiated at 20 mg, with dose titration every 4 weeks to a maximum of 80 mg daily, as tolerated. The primary objective will be to determine whether fluoxetine leads to improvement in PVR; secondary endpoints include 6MWD, quality of life, functional class and safety.

Study Methods:

Medication: 18 patients will receive fluoxetine. Dosing will be as descripted below:

- Week 1-4: 20 mg daily
- Week 5-8: 40 mg daily
- Week 9-12: 60 mg daily
- Week 13-24: 80 mg daily

Fluoxetine details:

Compounding: Prescription for fluoxetine will be sent to Walgreens pharmacy here at UTSW at the time of patient enrollment. 20 mg pills will be procured initially, and dosing will therefore be 1, 2, 3 or 4 pills daily. Fluoxetine is also available in a 40 mg pill, so that once a stable dose is reached patients will be transitioned to 20 mg daily (one 20 mg pill), 40 mg daily (one 40 mg pill), 60 mg daily (one 20 mg and one 40 mg pill) or 80 mg daily (two 40 mg pills). The maximum (fastest) rate of titration is the schedule above. Patients will follow the schedule as long as having no more than mild side effects. Slower up-titration will be allowed, and down-titration will also be allowed. However, by 16 weeks, a stable and final treatment dose must be reached. At this point no additional upward titrations will be allowed; down- titration for new onset side effects will still be permissible but this is anticipated to be uncommon.

Dose selection: Eighty mg is the maximum approved dose of fluoxetine, and this dose was chosen based on animal studies showing better responses at higher doses [11]. We anticipate that this will be tolerated in approximately 50% of fluoxetine patients, and that most of the remaining patients will tolerate one of the lower doses with ~10-20% drop out rate. These estimates are based on the tolerability of these medications in general, drop-out rates in PAH studies, and our

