- Plasma and serum will be banked for future non-genetic studies including p-selectin, soluble CD 40L, beta-thromboglobulin. A total of 20 ml will be drawn for these studies at visit 24 or end of study

Study procedures - timeline

During screening, inclusion/exclusion criteria will be reviewed and if met, informed consent will be obtained. Patients will be seen by the MD or nurse practitioner and coordinator at each visit, with tests as indicated in the chart. All visits and study procedures should be within +/- 7 days.

Table: Study Visits for Clinical Trial of Fluoxetine							
	Base -line	Week 1	Week 4	Week 8	Week 12	Week 18	Week 24
Phone call		Х					
Clinic visit / vitals / exam	Х		Х	Х	Х	Х	Х
6MWD, WHO Class	Х		Х	Х	Х	Х	Х
QIDS-SR	Х				Х		Х

SF-36	Х				Х		Х
Other QOL	Х				Х		Х
24-hr Urine / blood- work	Х						Х
Right Heart	Х						Х
Catheterization							
Fluoxetine (mg)	Start 20 mg	20 mg	40 mg	60 mg	80 mg	80 mg	80 mg
Table: Medication doses increase every 4 weeks, as tolerated. Pregnancy testing (when							
appropriate) will also be done at entry and prior to caths. 6MWD: six minute walk distance. WHO:							
World Health Organization. QIDS-SR: Depression Scale.							

Controls: will undergo a spot urine 5-HIAA – creatinine level and blood banking

Early withdrawal: Patients exiting the study early for any reason will complete the week 24 procedures, whenever possible. This includes those who request study discontinuation (for side effects or other reasons) and those who worsen during the study and require additional medications. Discontinuation will ideally be gradual, to be accomplished when possible over up to 4 weeks.

Routine end of study: patients will be offered treatment with open-label fluoxetine.

Sub-Study Procedures:

Urine 5HIAA and creatinine - 18 clinical trial patients and 16 controls (unrelated family members) will undergo spot urine 5HIAA, tested in the clinical laboratory. Trial participants will undergo a repeat test at week 24. 5HIAA and creatinine are clinical tests that can be run at Mayo. Total volume will be 1 urine sample (at least 10 ml) and 1 blood sample for all (20 ml); for clinical trial patients this will be repeated at end of study.

Comparisons will be:

- 1. 5HIAA level: IPAH vs. control.
- 2. Correlations: baseline 5HIAA vs. baseline PVR and vs. change in PVR at 24 weeks, IPAH patients.
- 3. Change in 5HIAA level: baseline vs. week 24, IPAH patients.

Blood – platelet and endothelial activation and fluoxetine

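### The 80% power is stated for a between-group difference that this one-arm trial does not have; the plan neither names a paired test nor defines its 20% SD

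*Combined protocol and SAP*

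**What the plan says.** The Concise Summary describes the design: "This is a phase II single open-label study enrolling 18 patients with PAH". All of them receive fluoxetine. The other participants are 16 healthy controls, and the study timeline limits their part: "Controls: will undergo a spot urine 5-HIAA" with creatinine, plus banked blood. They have no catheterization and so no PVR.

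Under Statistical Analysis, Aim 1, the primary endpoint (item 2) is the change in PVR from baseline to end of study. Item 5 says "All statistical testing will be baseline vs. follow-up at 24 weeks". For the test it says that Student's "t-tests will be used for significance testing if the data are normally distributed with no missing data". If data are missing because of drop-out or non-completion, "patients with worsening symptoms will be assigned worst rank, and a Wilcoxon rank sum test will be used".

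Item 6 assumes a baseline PVR of 9 Wood units and a 20% improvement, and adds: "We also anticipate a standard deviation of 20% of baseline PVR". It concludes: "With 16 patients completing, this study will have 80% power" at alpha 0.05 "to detect a between-group difference assuming 20% improvement with fluoxetine". It does not give the sidedness of the test or the correlation between visits.

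**The concern.** The power statement describes a comparison that the trial cannot make for its primary endpoint. It is also the only justification given for 16 completers and 18 enrolled, and the Completion paragraph under Other Potential Problems relies on it when it accepts two patients without a second catheterization.

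Two definitions that would let a reader rebuild the figure are absent. The t-test is not called paired, and the 20% SD could be the SD of within-patient change or the SD of PVR at a single visit. These give quite different power for the same 16 patients. The fallback test adds to the doubt, because the rank sum test is for independent samples while the data are pairs. An analyst who followed the named tests literally could run an unpaired analysis.

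**Working it through.** **Inputs from item 6.** Effect 20% of baseline (1.8 of 9 Wood units); SD 20% of baseline (also 1.8); alpha 0.05; 16 completers. The standardized effect is 20/20 = 1. Two-sided testing is my assumption.

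**Step 1: reproduce the 80%.** For two independent samples, the normal formula gives n per sample = 2 × (1.960 + 0.842)² / 1² = 15.7, rounded up to 16. With 16 per sample:
- normal approximation: Φ(√(16/2) − 1.960) = Φ(0.868) = 80.7%
- noncentral t, 30 df: 78.1%
- the same t-test one-sided: 86.8%, which does not match

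The stated 80% is therefore what two unrelated samples of 16 give with a two-sided test.

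**Step 2: paired t-test, 20% as the SD of change.** Noncentrality = √16 × 20/20 = 4, with 15 df. Power is 96.2%.

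**Step 3: paired t-test, 20% as the SD at each visit.** SD of change = 20 × √(2(1 − ρ)). The correlations ρ are assumed, since the plan gives none.

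| ρ | SD of change (% of baseline) | Power, n = 16 |
|---|---|---|
| 0 | 28.3 | 75% |
| 0.3 | 23.7 | 88% |
| 0.5 | 20.0 | 96% |
| 0.7 | 15.5 | over 99% |

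At ρ = 0 the normal approximation for the paired test is Φ(4/√2 − 1.960) = Φ(0.868) = 80.7%, identical to Step 1. Two independent samples and two uncorrelated visits are the same calculation.

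**Step 4: where the paired test falls below 80%.** Solving the noncentral t for 80% with n = 16 gives a standardized effect of 0.749. The SD of change is then 20/0.749 = 26.7% of baseline, or ρ of about 0.11 on the per-visit reading.

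**Step 5: an unpaired t-test on paired data.** By simulation with per-visit SD 20% and ρ = 0.5, the unpaired test has a true type I error of about 0.8% and 85% power. The paired test has 5% and 96%.

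**Step 6: the fallback with worst-ranked patients.** This is simulated with normal data and exact critical values. The SD of change is held at 20%, and worst-ranked follow-up values are set above all others. Signed-rank power is about 95% with none worst-ranked (16 measured), 83% with one (17 measured) and 28% with two (16 measured). Rank sum power depends instead on the per-visit SD. With two worst-ranked:

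| Per-visit SD (assumed) | ρ = 1 − 20²/(2 × SD²) | Signed-rank | Rank sum |
|---|---|---|---|
| 20% | 0.50 | about 28% | about 42% |
| 25% | 0.68 | about 28% | about 17% |
| 30% | 0.78 | about 28% | about 6% |

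The order of the two tests reverses between a per-visit SD of 20% and one of 25%.

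**The case against.** The best defence is that the endpoint is a change and all testing is baseline against follow-up, so pairing is implied and the between-group phrase is loose wording. The stated 80% can also be read as a conservative figure for the planned comparison with the visits taken as uncorrelated; Step 3 shows that the normal approximation then gives 80.7%. Both points stand. A reader might infer that 80% cannot be the power of a within-patient test, and the calculation does not support that. What remains is that the plan does not say this was intended, and that its named fallback is an unpaired test, which points away from pairing.

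A reader might also infer that an unpaired test would produce false positives. On positively correlated visits it is conservative, so the cost is lost power.

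The SD is attributed to references 41 to 47, which were not available here. The fair statement is that the protocol text does not define it, not that its authors had no definition.

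On drop-out, the plan asks early leavers, including those who worsen, for the end-of-study procedures, and lets enrollment grow so that 16 complete. Two worst-ranked patients may therefore be uncommon.

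**Conclusion.** The point holds as a fault of wording and definition in the primary power statement. The between-group difference does not exist for PVR. The stated 80% corresponds to two uncorrelated samples of 16. The paired analysis that the endpoint implies has 96% power if 20% is the SD of change, and 75% to over 99% for assumed correlations of 0 to 0.7 if 20% is the per-visit SD. These figures assume normal data and two-sided testing.

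A tempting stronger reading is that the trial is too small. The documents do not support it: power falls below 80% only with an SD of change above about 26.7% of baseline, a value that the plan nowhere gives. A second is that the figure was left over from a two-arm design. The safety monitoring section does plan adverse-event tables split by assigned group, which would fit, but the documents do not show the origin of the calculation.

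**What to change.** 1. In item 6, delete the between-group wording. In item 5, state a paired, two-sided t-test on within-patient change in PVR.
2. Say whether 20% is the SD of within-patient change or the SD at each visit. If it is the latter, give the correlation as well. Identify which of the cited references supports it.
3. Restate the power on that basis. For example: a paired two-sided t-test at 0.05 on 16 completers has 96% power for a mean 20% fall in PVR, taking the SD of within-patient change as 20% of baseline. Label any other SD as an assumption.
4. For change in PVR, replace the rank sum test with the Wilcoxon signed-rank test.
5. In the Completion paragraph, note that the two-drop-out allowance assumes drop-outs who are not worst-ranked.

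Keep the sample size. One clerical correction belongs in the same paragraph: 2/18 is 11.1%, while the printed 12.5% is 2/16.

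Items 1 to 3 and 5 cost wording and one short recalculation; the headline figure may rise or fall once the SD is defined. Item 4 changes the fallback test for the primary endpoint, so it needs an amendment before analysis. Its downside is that signed-rank power is only about 28% with two worst-ranked patients at an SD of change of 20%. Whether rank sum would do better depends on the per-visit SD, so the protocol should state no fixed ordering of the two tests.
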